9. STUDY CALENDAR

	Baseline Screening*	SRS (stereotactic radiosurgery) *	1 Month Follow Up ^{1*}	3 Month Follow Up ^{1*}	6 Month Follow Up ^{1*}	9 Month Follow Up ^{1*}	12 Month Follow Up ^{2*}
	Within 30 days of SRS	Gamma Knife or Linear Accelerator (LINAC)	30 days post SRS	90 days post SRS	180 days post SRS	270 days post SRS	1 years post SRS
Radiation Oncology consult and consent	X						
Medical History (including steroid usage)	X		X	X	X	X	X
Physical Examination	X		X	X	X	X	X
Vitals: weight/ht. BP ⁷	X	X	X	X	X	X	X
ds-GPA ⁵	X						
Diagnostic MRI Brain ⁶	X						
KPS	X						
MRI Brain Planning Scan ⁴		X					
ALC	X						
Toxicity assessment			X	X	X	X	X ⁸
MRI Brain with and without contrast ³			X	X	X	X	X

Footnotes:

1. Variations of +/- 30 days from the scheduled visit are permitted
2. After 12-months post-SRS, subjects will be followed at physician's discretion, approximately every 3-6 months per standard of care. Any MRI Brain, physical exam or vitals obtained at these appointments will be gathered. However, if these procedures are not performed per standard of care, this will not be a deviation.
3. MRI Brain performed at Indiana University will have sequences including contrast, no contrast, FLAIR, DTI and PWI. If patient receives MRI Brain outside of Indiana University, a minimum of contrast, no contrast and FLAIR will need to be obtained and all sequences mentioned above are encouraged.
4. Variations of -30 days from the scheduled visit are permitted for linear accelerator based SRS, and may include the baseline screening MRI at the treating radiation oncologist's discretion.
5. Will be calculated using www.brainmetgpa.com tool
6. Diagnostic brain MRI is considered standard of care and will be performed as part of standard of care if subjects have not already undergone the procedure prior to enrollment.
7. Height is only required at the baseline screening visit.
8. After 12 months, only clinically relevant AEs will be recorded.

* Subjects may be treated multiple times. Subjects cannot be enrolled if the treatment will have a dose overlap within the target from prior treatments of 20% or greater. Once it is determined that they will receive treatment if they are in follow-up, they will be enrolled onto cohort 2 and re-start all procedures beginning with baseline screening.

TREATMENT DOSE AND DELIVERY

The total radiosurgery dose will be specified according to tumor size as noted in Table 1. All patients will be treated to this dose in one session.

Table 1: RADREMI Dose Criteria

Maximum Tumor Diameter	Prescribed Dose
≤ 20 mm	18 Gy
21 – 30 mm	14 Gy
31 – 40 mm	12 Gy

FDA-approved stereotactic localization procedures for imaging and treatment delivery will be used. With radiosurgery treatments using the Leksell Gamma Knife Perfexion®, target localization will be performed using the head frame coordinate system. The Leksell GammaPlan® will be used to generate the treatment plan with respect to the coordinate system created by localization. Target volume and isocenter determination will be based on an MRI Brain scan with the patient's head in a stereotactic frame. The imaging study used to deliver the radiosurgical treatment must be the same as used to determine the size of the metastatic lesion(s). Stereotactic MRI slice thickness may not exceed 3 mm. The target volume will include the enhancing portion of the metastatic lesion. Surrounding areas of edema will not be considered part of the target volume.

Linear accelerator based stereotactic localization will be performed using the Encompass® SRS thermoplastic mask immobilization system. The patient will undergo a 1mm slice thickness helical CT scan that will be fused with the MRI brain T1-weighted post-contrast axial scan used for target delineation. The CT-MRI fusion maximum correlation error must be less than 1.5mm. The imaging study used to deliver the radiosurgical treatment must be the same as used to determine the size of the metastatic lesion(s). Stereotactic MRI slice thickness may not exceed 3 mm. The target volume will include the enhancing portion of the metastatic lesion. Surrounding areas of edema will not be considered part of the target volume.

The dose will be prescribed to the isodose surface (50 – 90%), which encompasses the margin of the metastasis, as defined by the imaging studies. The 100% dose will be recorded for each patient.

For patients with multiple brain metastases, stereotactic radiosurgery will be delivered to each lesion that has not previously undergone stereotactic radiosurgery. The prescribed dose will be according to the RADREMI dosing schema as described in Table 1 above. Due to the volumetric summation constraint for the remaining metastases, no single lesion greater than 4cm will be allowed on study, and, therefore, the above dose prescriptions can be used. If any two lesions are within 0.8 to 2 cm of each other, the intervening midplane dose will not exceed 13 Gy. This may require treating each respective target with a lesser dose than dictated by the above table. This is designated to minimize toxicity in patients.

Isodose distributions must be calculated, and the prescription isodose line clearly designated, for each target lesion in all planes.

Table 2: Critical Structures [36]

Structure	Maximum critical volume above threshold	Threshold dose (Gy)	Max Point Dose (Gy)
Optic pathway	<0.2 cc	8	10
Brainstem	<0.5 cc	10	15
Cochlea	N/A	N/A	9
Medulla	<1.2 cc	7	

The dose to the above structures must meet constraints as designated by TG-101; the small size of the cochlea allows for only a max point dose and not a maximum critical volume above threshold or a threshold dose (Benedict et al., 2010). If the above constraints cannot be met utilizing the prescribed radiosurgery dose Table 1, then the highest dose to the target volume will be used such that constraints can be met. This will be considered a minor deviation.

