4. OUTCOME MEASURES

4.1 Primary Outcome Measure

6 month symptomatic radiation necrosis, defined as a 6-month rate of clinical symptomatology requiring steroid administration (i.e. Decadron) and/or operative intervention concomitant with advanced and routine brain imaging findings consistent with radiation necrosis. Follow-up MRIs will be fused with the planning scan for this assessment.

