8.6 Long Term Follow up

Subjects will be followed approximately every 3 months (+/- 30 days) after SRS for 1 year. A detailed medical history (including necessity of any steroid administration), toxicity assessment and physical examination including vital signs will be performed at each visit. Each follow-up over this time period will also include a Brain MRI with the following sequences: without contrast, with contrast, FLAIR, Diffusion Tensor Imaging (DTI) and Perfusion Weighted Imaging (PWI). The MRI will be analyzed per RANO BM criteria (Section 11) for assessment of local control. The MRI will also be analyzed for radiation necrosis as discussed in Section 12. Neurologic status will be assessed using the Neurologic Assessment in Neuro-Oncology (NANO) scale (Nayak et al., 2017).

After the 1-year (12-month) follow-up period, subjects will be followed according to their treating physician per standard of care every 3-6 months. MRI Brain obtained during this time period may be used for assessment of primary and secondary endpoints; however, are not mandated to be obtained at particular time intervals. Patients who are unable to travel to Indiana University for follow-up appointments will have records sent to Indiana University at each follow-up.

From year 2-5, the follow up period will be determined by their treating physician per standard of care, generally every 3-6 months. MRIs will be obtained per treating physician discretion.

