11. RADIATION NECROSIS

12.1 Radiographic Radiation Necrosis

Assessment for radiation necrosis will be done based on the contrast-enhanced, FLAIR, Diffusion tensor imaging (DTI) and Perfusion weighted imaging (PWI) MRI sequences. Radiation necrosis is typically a contrast enhancing lesion with surrounding edema noted on contrast-enhanced MRI and FLAIR respectively; however, this is difficult to distinguish from recurrent tumor. Therefore, DTI and PWI sequences will be analyzed as well. DTI uses fractional anisotropy that reflects the preferential direction of water diffusion along white matter tracks. Fractional anisotropy in radiation necrosis is lower than that for recurrent tumor due to lack of normal axonal fibers or cells within the necrotic area as compared to partially functioning axonal fibers and cells associated with recurrent tumor (Shah et al., 2012). PWI

assesses intra-lesional and peri-lesional cerebral blood volume. Recurrent tumor is more likely to be associated with higher cerebral blood volume than radiation necrosis as radiation necrosis is devoid of vasculature. The percentage of signal recovery $\geq 76.3\%$ has a sensitivity of 96% and specificity of 100% for radiation necrosis as noted on PWI. (Barajas et al., 2009).

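### The imaging needed to call the primary event is defined inconsistently, so symptomatic radiation necrosis can be classified differently depending on where the MRI was done

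*Combined protocol and SAP*

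**What the plan says.** The sections that bear on imaging for the primary event do not agree.

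- **Section 4.1 (and 3.1):** the event is symptoms needing a listed treatment "concomitant with advanced and routine brain imaging findings consistent with radiation necrosis".
- **Section 12.1:** "Assessment for radiation necrosis will be done based on the contrast-enhanced, FLAIR, Diffusion tensor imaging (DTI) and Perfusion weighted imaging (PWI) MRI sequences". The reason given is that enhancement with edema is typical of necrosis; "however, this is difficult to distinguish from recurrent tumor. Therefore, DTI and PWI sequences will be analyzed as well".
- **Section 12.2:** symptomatic necrosis is assessed among patients who already meet the radiographic criteria, so Section 12.1 feeds the primary endpoint.
- **Section 8.6:** DTI and PWI are listed for each follow-up MRI in the first year, with no exception by location.
- **Section 9, footnote 3:** for an MRI outside Indiana University, "a minimum of contrast, no contrast and FLAIR will need to be obtained", while "all sequences mentioned above are encouraged".
- **Section 2 (Summary and Rationale) and Section 4.2, item 2:** necrosis imaging is an and/or list of MRI, perfusion, spectroscopy and PET. DTI is not named.

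Section 6 describes a multi-site study. Section 14.1 says missing data are not imputed. Section 14.4 allows for up to 5% of patients not evaluable for symptomatic necrosis but does not define evaluable.

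**The concern.** Take a patient with new symptoms, a treatment that counts toward the endpoint, and enhancement with edema at a treated site, scanned only to the footnote 3 minimum. Under Section 4.1 as worded there are no advanced findings, so the definition is not met. Under Sections 2 and 4.2, MRI alone could support the call. Two assessors following the protocol could classify this patient in opposite ways, and which patients are affected depends on where the scan was done.

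The decision rests on a small count: Section 14.4 claims success with at most 4 events in 40 patients. In a single-arm study against a fixed 16%, no control arm shares the ascertainment error. Each event lost to an imaging technicality moves the result toward success.

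**Working it through.** **Inputs.** From Section 14.4: historical rate 16%, expected rate 5%, 40 evaluable patients, success if at most 4 events. Two quantities are assumptions, because the documents give neither: *f*, the share of patients assessed on minimum scans, and *s*, the probability that a true event among them is still called.

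**The plan's own design first.** With X binomial (40, p), the printed rule gives P(X ≤ 4) = 0.211 at p = 0.16 and 0.952 at p = 0.05. The sample size of 40 does reproduce as the smallest n with type I error at most 10% and power at least 80%, but with a cutoff of at most 3 events (0.098 and 0.862). The printed cutoff of 4 therefore misses the stated 10%. That is a separate matter; here 0.211 serves only as the starting point.

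**Effect of lost events.** Apparent rate = 0.16 × (1 − f + f·s). Example: f = 0.25 and s = 0.5 give 0.16 × 0.875 = 0.14, and P(X ≤ 4) = 0.324.

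P(success) at a true rate of 16%, cutoff 4:

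| f | s = 0.8 | s = 0.5 | s = 0 |
|---|---|---|---|
| 0 | 0.211 | 0.211 | 0.211 |
| 10% | 0.227 | 0.252 | 0.299 |
| 25% | 0.252 | 0.324 | 0.467 |
| 50% | 0.299 | 0.467 | 0.787 |

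The effect does not depend on the cutoff problem. With at most 3 events and s = 0, the values are 0.098 (f = 0), 0.153 (10%), 0.277 (25%) and 0.601 (50%).

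**Effect in the other direction.** Suppose the looser wording is used, and recurrence treated with steroids is called necrosis in a share e of event-free patients on minimum scans. Apparent rate at a true 5% = 0.05 + f × e × 0.95. For e = 5% and 10% respectively, P(X ≤ 4) falls from 0.952 to 0.934 and 0.913 (f = 10%), 0.901 and 0.830 (f = 25%), or 0.830 and 0.650 (f = 50%).

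**Interim.** The Section 14.4 look tests a local control rate of at least 75% in 20 patients. P(X ≤ 11 | 20, 0.75) = 0.041, which stops the study; P(X ≤ 12) = 0.102, which does not. One necrosis case read as progression can therefore change that decision. This works toward early stopping, the opposite of the effect on the primary count.

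**The case against.** A reader might infer that necrosis cannot be called at all without DTI and PWI, and that the primary event is therefore undercounted at outside sites. The documents do not support either statement.

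- Sections 2 and 4.2 allow MRI or other modalities. Section 12.1 says the distinction from tumor is difficult, not impossible. It sets no DTI threshold and gives its perfusion figure as test accuracy, not as a case rule.
- No section scores missing sequences as no event. Section 14.4 leaves room for such a patient to be non-evaluable.
- Confusion with recurrence can raise the count as well as lower it.
- A symptomatic patient is likely to be worked up further. Section 8.4 permits additional imaging, and Section 11.2 item 4 names repeat scans, perfusion, spectroscopy, PET and pathology. The column s = 0 is thus a worst case.
- Footnote 3 turns on where the MRI is performed, not on the enrolling site. The sentence "Patients who are unable to travel to Indiana University for follow-up appointments will have records sent to Indiana University at each follow-up" sits in the paragraph on follow-up after 12 months, so it is weak evidence of outside scanning before the 6-month endpoint.

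All of this stands and limits the claim. It does not remove the inconsistency. The discretionary work-up in Section 8.4 is not required, and Section 11.2 itself calls standard MRI insufficient when treatment effect is suspected and asks for the distinguishing methods to be specified in advance. Treating such patients as non-evaluable would still take symptomatic cases out of the event count.

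**Conclusion.** The point holds as an inconsistency in the definition of the primary event, with no rule for patients who lack advanced imaging. Classification can differ by scan location. Under the literal Section 4.1 wording the error favours a success claim; under Sections 2 and 4.2 its direction is open. Undercounting is conditional, not established.

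The size cannot be fixed from the documents. At a true rate of 16%, the chance of success rises from 0.211 to between 0.227 and 0.299 if 10% of patients are on minimum scans, and to between 0.299 and 0.787 if half are. The lower ends assume that 80% of their events are still called, the upper ends that none are. The change should be made: the contradiction is in the current text, it reaches the primary decision, and removing it is cheap.

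**What to change.** 1. Reconcile Sections 2, 3.1, 4.1, 4.2, 8.6, 9 (footnote 3), 12.1 and 12.2 into one imaging definition of the primary event.
2. Record in the CRF which sequences were obtained at each follow-up MRI.
3. Classify as indeterminate any patient who has symptoms needing a treatment that defines the event and an imaging change at a treated site, but no advanced imaging or pathology to separate necrosis from tumor.
4. In Section 14.7, report the primary count and decision twice, with indeterminate cases as events and as non-events. State in advance that a success claim should hold when they count as events. Tabulate symptomatic necrosis by whether advanced sequences were available.

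Indeterminate cases should not simply be made events under a single definition. Section 10.1 provides for dexamethasone for peri-tumoral edema, so ordinary edema could become a primary event, and the power losses shown above would follow. Reporting both counts shows how far the conclusion depends on these cases.

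**Cost:** protocol and SAP wording, one CRF item and a little more analysis; no added scans or staff. The success claim may become harder to sustain if many cases are indeterminate.

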10.1 General Concomitant Medication and Supportive Care Guidelines

For patients presenting with signs and symptoms relatable to peri-tumoral edema, including but not limited to nausea and headaches, dexamethasone will be prescribed at a dose level per clinician judgement.

For patients presenting with seizure, anti-seizure medication will be prescribed at a dose level per clinician judgement. No specific type of anti-seizure medication is recommended or prohibited.

Each patient will be given a prescription for 1mg Ativan to be taken approximately 30 minutes prior to the procedure, or otherwise at the physician's discretion.

10. RESPONSE ASSESSMENT IN NEURO-ONCOLOGY BRAIN METASTASES (RANO-BM)

11.1 Definitions Associated with RANO-BM (Lin et al., 2015)

1. **Measurable disease** is defined as a contrast-enhancing lesion that can be accurately measured in at least one dimension, with a minimum size of 3 mm, and is visible on three or more axial slices that are preferably 1 mm or less apart with 0 mm skip (and ideally ≤ 1.5 mm apart with 0 mm skip).
 - a. Additionally, although the longest diameter in the plane of measurement is to be recorded, the diameter perpendicular to the longest diameter in the plane of measurement should be at least 3 mm for the lesion to be considered measurable.
 - i. Note: Recording of the 2nd dimension is at the radiologist's discretion, if measurable.
 - b. If the MRI is performed with thicker slices, the size of the measurable lesion at baseline should be at least double the slice thickness. Interslice gaps, if present, should also be considered in the determination of the minimum size of measurable lesions at baseline.

2. **Non-measurable disease** includes all other lesions, including lesions with longest dimension less than 3 mm, lesions with borders that cannot be reproducibly measured, dural metastases, bony skull metastases, cystic-only lesions, and leptomeningeal disease.

3. Methods of measurement

The same method of assessment and the same technique should be used to characterize each identified and reported lesion at baseline and during follow-up. Consistent use of imaging techniques across all imaging time points is important to ensure that the assessment of interval appearance, disappearance of lesions, or change in size is not affected by scan parameters such as slice thickness. Use of thin section imaging is particularly important for the assessment of lesions less than 3 mm in longest diameter or small changes in lesion size, or both.

Gadolinium-enhanced MRI is the most sensitive and reproducible method available to measure CNS lesions selected for response assessment. MRI is strongly encouraged as the default standard imaging technique, although CT with and without contrast could be considered in specific circumstances (e.g., countries with limited medical resources or contraindication for MRI).

4. Tumor response assessment

Only patients with measurable CNS disease at baseline should be included in protocols where objective CNS tumor response is the primary endpoint. For studies in which objective response is not the primary endpoint, the protocol must specify prospectively whether entry is restricted to those with measurable disease or if patients with non-measurable disease are also eligible.

- a. Assignment of CNS response is independent of systemic disease response. CNS lesions are to be assessed according to RANO-BM criteria, whereas non-CNS lesions would most typically be assessed according to RECIST 1.1 criteria.
- b. Generally, CNS lesions should initially be re-assessed by MRI at protocol-specified intervals 6–12 weeks apart, although there might be specific circumstances in which longer (or shorter) intervals are desirable. For patients who remain stable for extended periods of time, a longer interval between scans might be appropriate. All baseline assessments should be done as close as possible to the treatment start and no more than 4 weeks before the beginning of treatment.
- c. For previously treated lesions, we recommend documentation of how each lesion was previously treated (e.g., stereotactic radiosurgery, whole brain radiotherapy, surgical resection).
- d. When more than one measurable lesion in the CNS is present at baseline, all lesions up to a maximum of five CNS lesions should be identified as target lesions and will be recorded and measured at baseline. All measurements should be recorded in metric notation. Target lesions should be selected on the basis of

their size (longest diameter) and as those that can be measured reproducibly. For patients with recurrent disease who have multiple lesions, of which only one or two are increasing in size, the enlarging lesions should be prioritized as target lesions for the response assessment.

- e. Lesions with prior local treatment (i.e., stereotactic radiosurgery or surgical resection) can be considered measurable if progression has occurred since the time of local treatment. However, careful consideration should be given to lesions previously treated with stereotactic radiosurgery, in view of the possibility of treatment effect, which is discussed below. Whether such lesions can be considered measurable should be specified prospectively in the clinical protocol. If lesions not previously treated with local therapies are present, these are preferred for selection as target lesions.
- f. A sum of the diameters for all target lesions will be calculated and reported as the baseline sum of longest diameters. All other CNS lesions should be identified as non-target lesions and should also be recorded at baseline. Measurements are not required and these lesions should be classified as present, absent, or unequivocal progression, and followed up.

11.2 Response assessment of target and non-target lesions

Please see Table 3 and Table 4 for a partial summary of this section.

1. While on study, all CNS target lesions should have their actual measurement recorded, even if very small (e.g., 2 mm). If the lesion disappears, the value should be recorded as 0 mm. However, if the lesion is sufficiently small (but still present) to be assigned an exact measurement, a default value of 5 mm should be recorded on the case report form.
2. Lesions might coalesce during treatment. As lesions coalesce, a plane between them may be maintained that would aid in obtaining maximum longest diameter of each individual lesion. If the lesions have truly coalesced such that they are no longer separable, the vector of the longest diameter in this instance should be the maximum longest diameter for the coalesced lesion.
3. New lesions can appear during treatment. The finding of a new CNS lesion should be unequivocal and not due to technical or slice variation. A new lesion is one that was not present on prior scans.
 - i. If the MRI is obtained with slice thickness of 1.5 mm or less, the new lesion should also be visible in axial, coronal, and sagittal reconstructions of 1.5 mm or thinner projections.
 - ii. If a new lesion is equivocal, for example because of its small size (i.e., ≤ 3 mm), continued therapy can be considered, and a follow-up assessment will clarify if it really is new disease. If repeated scans confirm a new lesion, progression should be declared using the date of the initial scan showing the new lesion.

- iii. In the case of immunotherapy, however, new lesions alone cannot constitute progressive disease (see below).
4. The RANO-BM group acknowledges the case of patients who have been treated with stereotactic radiosurgery or immunotherapy-based approaches, for whom there has been radiographical evidence of enlargement of target and non-target lesions, which do not necessarily represent tumor progression. If radiographical evidence of progression exists, but clinical evidence indicates that the radiological changes are due to treatment effect (and not to progression of cancer), additional evidence is needed to distinguish between true progression and treatment effect, in which case standard MRI alone is insufficient. The methods used to distinguish between true progression and treatment effect should be specified prospectively in the clinical protocol. Patients can be continued on protocol therapy pending further investigation with one or more of the following options.

The scan can be repeated at the next protocol-scheduled assessment or sooner, and generally within about 6 weeks. An investigator can choose a shorter time interval if progressive symptoms or other clinical concerns arise. Continued tumor growth might be consistent with radiographical progression, in which case the patient should leave the study. Stabilization and shrinkage of a lesion can be consistent with treatment effect, in which case the patient can stay in the study. For patients with equivocal results even on the next restaging scan, the scan can be repeated again at a subsequent protocol-scheduled assessment or sooner, although surgery or use of an advanced imaging modality (in the case of stereotactic radiosurgery), or both, are strongly encouraged. Surgical pathology can be obtained via biopsy or resection.

- i. For lesions treated by stereotactic radiosurgery, additional evidence of tumor progression or treatment effect (radionecrosis) can be acquired with an advanced imaging modality, such as perfusion MRI, magnetic resonance spectroscopy, or ¹⁸FLT or ¹⁸FDG PET. Current recommendations suggest involving a multidisciplinary team to decide on the appropriate next step. Irrespective of the additional testing obtained, if subsequent testing shows that progression has occurred, the date of progression should be recorded as the date of the scan this issue was first raised.

Patients can also have an equivocal finding on a scan (e.g., a small lesion that is not clearly new). Continued treatment is permissible until the next protocol-scheduled assessment. If the subsequent assessment shows that progression has indeed occurred, the date of progression should be recorded as the date of the initial scan where progression was suspected.

- ii. In patients receiving immunotherapy-based treatment, an initial increase in the number and size of metastases can be followed by radiographical stabilization or regression. This pattern might be related to the mechanism of action of immunotherapy, including immune infiltrates, and the time to mount an effective immune response. Thus, progressive disease should not be solely defined by the

appearance of new lesions but rather as a minimum 20% increase in the sum longest diameter of CNS target and new lesions, as unequivocal progression of existing enhancing non-target CNS lesions, as unequivocal progression of existing non-enhancing (T2/FLAIR) CNS lesions, or as clinical decline related to the tumor. If immune response-related radiographical changes are suspected, we advise to not change treatment until a short interval scan is obtained. If the subsequent assessment confirms that progression has indeed occurred, the date of progression should be recorded as the date of the initial scan where progression was suspected.

Note that the advanced imaging modalities discussed for treatment effect above have not been extensively studied with regards to immunotherapy-based approaches and therefore cannot be recommended to distinguish between tumor progression and immune-related changes at present.

5. In the absence of clinical deterioration related to the tumor, an increase in corticosteroid dose alone should not be used as a sole determinant of progression. Patients with stable imaging results and whose corticosteroid dose has increased for reasons other than clinical deterioration related to the tumor do not qualify as having stable disease or progression. These patients should be observed closely, and if their corticosteroid dose can be reduced back to baseline, they will be considered as having stable disease, but if further clinical deterioration related to the tumor becomes apparent, they will be considered as having progression.

The definition of clinical deterioration is left to the discretion of the treating physician, but it is recommended that patients who have a decrease in score on the Karnofsky performances scale from 100 or 90 to 70 points or less, a decrease of minimum 20 points from 80 or less, or a decrease from any baseline to 50 points or less, for at least 7 days, be considered as having neurological deterioration, unless this functional impairment is attributable to comorbid events, treatment-related toxicity, or changes in corticosteroid dose.

Table 3. Response assessment of target and non-target lesions (Lin et al., 2015)

Target lesions

Complete response

Disappearance of CNS target lesion(s) sustained for at least 4 weeks; with no new lesions, no use of corticosteroids and patient is stable or improved clinically.

Partial response

At least a 30% decrease in the sum longest diameter of CNS target lesion(s), taking as reference the baseline sum longest diameter sustained for at least 4 weeks; no new lesions; stable to decreased corticosteroid dose; stable or improved clinically.

Progressive disease

At least a 20% increase in the sum longest diameter of CNS target lesion(s), taking as reference the smallest sum on study (this includes the baseline sum if that is the smallest on study). In addition to the relative increase of 20%, at least one lesion must increase by an absolute value of 5 mm or more to be considered progression.

Stable disease

Neither sufficient shrinkage to qualify for partial response nor sufficient increase to qualify for progressive disease, taking as reference the smallest sum longest diameter while on study.
Non-target lesions
Non-target lesions should be assessed qualitatively at each of the time points specified in the protocol.
Complete response
Requires all of the following: disappearance of all enhancing CNS non-target lesions, no new CNS lesions.
Non-complete response or non-progressive disease
Persistence of one or more non-target CNS lesion or lesions.
Progressive disease
Any of the following: unequivocal progression of existing enhancing non-target CNS lesions, new lesion(s) (except while on immunotherapy-based treatment), or unequivocal progression of existing tumor-related non-enhancing (T2/FLAIR) CNS lesions. In the case of immunotherapy-based treatment, new lesions alone may not constitute progressive disease.

